8.8.3. Safeguards, Security, and Traceability of Contacts

Operators of a call centre specialised in health surveys will be assigned to the project and trained on the survey methodology prior to fieldwork. The postal mailings, email contacts, and phone calls will be traced using management software.¹⁶

Access to the web survey interface will be strictly limited to the invited HCPs, with the possibility to participate only once, which will be monitored using a traceability system. The same procedure will be followed if the invited HCPs take the survey over the phone.

8.9. Limitations of the Research Methods

8.9.1. Absence of Baseline

The Sponsor's ability to measure the extent to which HCPs' knowledge or behaviours can be attributed to the aRMM program will be limited. As the original aRMM materials were distributed at the time of initial marketing authorisation, no baseline measures of HCPs' knowledge or behaviour in the absence of the aRMM materials will be available. However, the knowledge and behaviour of the HCPs who self-reported having received and/or utilised the aRMM materials can be compared with the knowledge and behaviour of the HCPs who self-reported having *not* received and/or utilised the aRMM materials, provided that there is a sufficient number of respondents across both strata.

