4. Self-reported adherence to the risk minimisation practices recommended in the aRMM materials (e.g., provision of patient counselling and the alert card to patients, patient screening, laboratory monitoring recommendations, and limitations of use).

- HCPs providing desirable responses for each adherence question, or each adherence response option associated with a survey question (as applicable).

	RA/PsA survey	UC survey

 HCPs providing desirable responses to ≥70% to <80% of the adherence questions 	Providing desirable responses to 12-13 out of 17 adherence questions	Providing desirable responses to 12-13 out of 17 adherence questions

 HCPs providing desirable responses to ≥80% to <90% of the adherence questions 	Providing desirable responses to 14-15 out of 17 (adherence questions)	Providing desirable responses to 14-15 out of 17 adherence questions

 HCPs providing desirable responses to ≥90% to <100% of the adherence questions 	Providing desirable responses to 16 out of 17 adherence questions	Providing desirable responses to 16 out of 17 adherence questions

 HCPs providing desirable responses to 100% of the adherence questions 	Providing desirable responses to 17 out of 17 adherence questions	Providing desirable responses to 17 out of 17 adherence questions

Note: There are 17 questions that ascertain adherence to the risk minimisation practices recommended in the aRMM materials in both the RA/PsA and UC surveys. One of these

questions is also counted as a utilisation question (see Table 3 [RA/PsA survey] and Table 4 [UC survey]).

5. Effectiveness of the aRMM program in *each* of the following 4 domains:

	RA/PsA survey	UC survey

 Awareness (Receipt) ever 	
≥80% of HCPs reporting that they received 4 out of the 4 (100%) aRMM materials⁵ in all countries, except for Germany⁶
 
≥80% of HCPs reporting that they received 3 out of the 3 (100%) aRMM materials⁶ in Germany
	
≥80% of HCPs reporting that they received 4 out of the 4 (100%) aRMM materials⁵ in all countries, except for Germany⁶
 
≥80% of HCPs reporting that they received 3 out of the 3 (100%) aRMM materials in Germany⁶

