
 Awareness (Receipt) after February 2020 	
≥80% of HCPs reporting that they received 4 out of the 4 (100%) aRMM materials⁵ in all countries, except for Germany
 
≥80% of HCPs reporting that they received 3 out of the 3 (100%) aRMM materials⁶ in Germany
	
≥80% of HCPs reporting that they received 4 out of the 4 (100%) aRMM materials⁵ in all countries, except for Germany
 
≥80% of HCPs reporting that they received 3 out of the 3 (100%) aRMM materials⁶ in Germany

 Knowledge 	
≥80% of HCPs correctly answering ≥14 out of 18 (≥78% [or approximately 80%]) of the knowledge questions
	
≥80% of HCPs correctly answering ≥16 out of 20 (≥80%) of the knowledge questions

 Adherence 	
≥80% of HCPs providing desirable responses for ≥14 out of 17 (≥82% [or approximately 80%]) of the adherence questions
	
≥80% of HCPs providing desirable responses for ≥14 out of 17 (≥82% [or approximately 80%]) of the adherence questions

Note: The measures of effectiveness in each of the 4 domains listed above will be calculated variables.

⁵ The 4 aRMM materials include: the Xeljanz Prescriber Brochure, the Xeljanz Prescriber Treatment Initiation Checklist, the Xeljanz Prescriber Treatment Maintenance Checklist, and the Xeljanz Patient Alert Card. As the Xeljanz Prescriber Website is a repository for the aRMM materials, rather than a tool in and of itself, awareness of the Xeljanz Prescriber Website will not be considered when evaluating the effectiveness of the entire aRMM program.

⁶ The 3 aRMM materials include: the Xeljanz Prescriber Brochure, the Xeljanz Prescriber Treatment Initiation and Maintenance Checklist, and the Xeljanz Patient Alert Card. As the Xeljanz Prescriber Website is a repository for the aRMM materials, rather than a tool in and of itself, awareness of the Xeljanz Prescriber Website will not be considered when evaluating the effectiveness of the entire aRMM program.

6. Attitude toward the aRMM materials (i.e., how useful the HCPs find the various aRMM materials in their practice).

- There are 5 survey questions (1 question for each of the aRMM materials plus 1 question for the Xeljanz Prescriber Website) that ascertain HCPs' attitudes towards the aRMM materials, except for Germany, which has 4 questions.

7. Source of HCPs' information on the safety of Xeljanz.

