8.3.1. Mapping of Select Variables to Survey Questions

A cross-walk of the survey questions associated with each key risk message assessed in the RA/PsA and UC surveys are presented in Appendix 3 and Appendix 4 (Key Risk Messages for the RA/PsA survey and the UC survey, respectively).

The number of survey questions associated with HCPs' self-reported awareness (receipt) and utilisation of the aRMM materials and Xeljanz Prescriber Website for both the RA/PsA and UC surveys is listed in Table 2.

Table 2. Number of Survey Questions Associated with Awareness (Receipt) and Utilisation of the aRMM Materials for both the RA/PsA and UC Surveys

Concept	Total number of survey questions
aRMM materials and Xeljanz Prescriber Website awareness (receipt), ever and after February 2020	9 (7 for Germany)
aRMM materials and Xeljanz Prescriber Website utilisation	5 ^b
TOTAL	14 (12 for Germany)

Abbreviations: aRMM = additional risk minimisation measures; PsA = psoriatic arthritis; RA = rheumatoid arthritis; UC = ulcerative colitis.

- There are 4 aRMM materials in all countries, except for Germany: the Xeljanz Prescriber Brochure, the Xeljanz Prescriber Initiation Checklist, the Xeljanz Prescriber Maintenance Checklist, and the Xeljanz Patient Alert Card; there is also the Xeljanz Prescriber Website, a repository for the aRMM materials. In Germany, there are 3 aRMM materials: the Xeljanz Prescriber Brochure, the Xeljanz Prescriber Initiation and Maintenance Checklist, and the Xeljanz Patient Alert Card; there is also the Xeljanz Prescriber Website, a repository for the aRMM materials.
- Survey question 11a. In your clinical practice, how frequently do you “give the patient alert card to the patient” is counted as both a utilisation and an adherence (Table 3 [RA/PsA survey] and Table 4 [UC survey]) question.

As shown in Table 3, each key risk message has at least 1 corresponding RA/PsA survey question. There is a total of 35 survey questions related to the key risk messages. Eighteen of these 35 questions are **knowledge questions** and 17 of the 35 are **adherence questions**. For survey questions consisting of several response options, each individual response option is counted as a separate question since they can be viewed as distinct sub-messages pertaining to the key risk messages.

Table 3. Key Risk Messages and Associated Number of RA/PsA Survey Questions, Stratified by Type of Question (i.e., Knowledge or Adherence)

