8.7. Data Analysis

8.7.1. General Statistical Consideration

Detailed methodology for summary and statistical analyses of data collected in this study will be documented in a statistical analysis plan (SAP), which will be dated, filed, and maintained by the Sponsor. The SAP may modify the analyses outlined in this protocol; any major modifications of primary endpoint definitions or their analyses will be reflected in a protocol amendment.

The data collected from the RA/PsA survey will be analysed separately from the data collected from the UC survey. For each survey (RA/PsA and UC), all primary analyses will be conducted using the *pooled* data from all countries, specialties (applies to the RA/PsA survey only), and indications (applies to the RA/PsA survey only), and will be descriptive in nature; no statistical comparisons within or between countries, specialties, and/or indications will be conducted. Only submitted and completed surveys—i.e., all of Questions of the survey (Appendix 1 and Appendix 2 [HCP Questionnaire for the RA/PsA survey and the UC survey, respectively]) answered (taking into account skip patterns) by HCPs eligible to participate in the survey—will be used in the analyses.

Categorical variables will be presented using frequencies and proportions. For most outcomes, associated 95% CIs will also be calculated; 95% CIs will *not* be calculated for outcomes such as attitude towards the aRMM materials and Xeljanz Prescribe Website and source of HCPs’ information on the safety of Xeljanz. Continuous variables will be presented using means, standard deviations (SDs), minimums, 25th percentiles, medians,

75th percentiles, and maximums. Depending on the sample size, stratification by country, number of patients treated with Xeljanz, experience prescribing Xeljanz (a proxy for indication), receipt and utilisation of the aRMM materials, and/or number of years in practice may be performed. The analysis may also be restricted to HCPs without prior experience as a healthcare professional in a Xeljanz clinical trial, if sample size is sufficient.

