Select the best response for each scenario: “I would discontinue tofacitinib,” “I would interrupt dosing,” “I would lower the dose,” OR “I would take no action.”

		I would discontinue tofacitinib	I would interrupt dosing	I would lower the dose	I would take no action
a	The patient’s neutrophil count is less than 0.50 cells x 10 ⁹ /L. This is confirmed by repeat testing.	•	○	○	○
b	The patient’s lymphocyte count is between 0.50-0.75 cells x 10 ⁹ /L. This is confirmed by repeat testing.	○	•	○	○
c	The patient develops a serious infection, an opportunistic infection or sepsis.	○	•	○	○
d	The patient develops severe hepatic impairment (Child Pugh C).	•	○	○	○
e	The patient’s haemoglobin level is <8 g/dl. This is confirmed by repeat testing.	○	•	○	○
f	The patient has a suspected venous thromboembolism (VTE).	•	○	○	○

Data: Single punch per row.

Data: Answer options will be displayed in a random order for each survey participant.

Answer: The black circles indicate a desired response.

090177e199ebc283\Approved\Approved On: 11-Apr-2022 22:32 (GMT)

[QUESTIONS ABOUT ADHERENCE TO KEY RISK MESSAGES FOR TOFACITINIB]

[QUESTION APPLIES TO ALL COUNTRIES]

Q11. In your clinical practice, how frequently do you perform each of these activities when **initiating treatment** with tofacitinib? Please select the best response: “Always,” “Sometimes,” or “Never”.

		Always	Sometimes	Never
a	Give the tofacitinib patient alert card to the patient.	•	•	○
b	Advise the patient to inform you immediately if they experience any of the symptoms on the tofacitinib patient alert card.	•	•	○
c	Advise patients to carry the tofacitinib patient alert card with them, particularly when they visit a doctor, a hospital, or Accident and Emergency.	•	•	○
d	Discuss the signs and symptoms of venous thromboembolism (VTE) with the patient.	•	•	○

Data: Multiple punch.

Answer: The black circles indicate a desired response.

090177e199ebc283\Approved\Approved On: 11-Apr-2022 22:32 (GMT)

[SOURCE OF HCPs' INFORMATION ON THE SAFETY OF TOFACITINIB]

[QUESTION APPLIES TO ALL COUNTRIES]

The final set of questions asks about sources of information on tofacitinib.

Q12. Which of the following is your **primary source** of safety and prescribing information for tofacitinib? Please select one.

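### The comparison by receipt or use of the materials is partly built in for adherence, because 3 of the 17 adherence items concern the alert card and one of them is also the card-utilisation variable

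*Protocol*

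**What the plan says.** Section 8.9.1 of the protocol states that "no baseline measures of HCPs' knowledge or behaviour in the absence of the aRMM materials will be available". In its place it says that "the knowledge and behaviour of the HCPs who self-reported having received and/or utilised the aRMM materials can be compared with the knowledge and behaviour" of HCPs who report not having received or used them, provided both groups are large enough. Section 8.7.1 makes this an option that depends on sample size: stratification by "receipt and utilisation of the aRMM materials, and/or number of years in practice may be performed".

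Section 8.3 defines the behaviour measure: "There are 17 questions that ascertain adherence to the risk minimisation practices" in both surveys. An HCP counts towards the adherence criterion by "providing desirable responses for ≥14 out of 17", and the criterion is met if at least 80% of HCPs do so.

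Three of the 17 items name the patient alert card (Q11 in Appendix 1; identical in Appendix 2):
- Q11a: "Give the tofacitinib patient alert card to the patient".
- Q11b: "Advise the patient to inform you immediately if they experience any of the symptoms on the tofacitinib patient alert card".
- Q11c: advising patients to carry the card.

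Always and Sometimes both count as desirable. Q11 has no filter on card receipt (Q16.1a) and no not-applicable option, and section 8.6.4 allows submission only when every question is answered. The follow-up questions on reading, using and rating each material, by contrast, are asked only of HCPs who report receiving it. The notes to Table 2 in section 8.3.1 say that Q11a "is counted as both a utilisation and an adherence" question.

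**The concern.** The card is one of the materials whose receipt and use define the comparison groups, and it is also the subject of three outcome items. An HCP without cards who truthfully answers Never to Q11a-c loses three points whatever their screening, testing or VTE counselling. If card use is the stratifier, the answer to Q11a fixes both the group and one point of the outcome.

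The protocol discloses the double role of Q11a. It nowhere separates the card items from the adherence score when strata are compared, and section 8.9.1 does not mention the overlap. The resulting gap always favours the programme, in the one contrast that stands in for a missing baseline. A reader could take a difference created by the item set as evidence that the materials changed practice more broadly.

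**Working it through.** **Inputs from the protocol.** Adherence items: Q8a-f (6), Q9a-g (7), Q11a-d (4), so 6 + 7 + 4 = 17, as stated. Pass mark: 14/17 = 82.4%, matching the stated ≥82%. Card items: Q11a, Q11b, Q11c. Remaining items: 17 − 3 = 14 (Q8a-f, Q9a-g, Q11d).

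**Ceiling.** An HCP who scores 0 on Q11a-c can reach at most 14/17. That is exactly the pass mark, so all 14 other items must be answered desirably.

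**Assumptions, not in the documents.** Items are independent, and each non-card item has the same probability p of a desirable response in both groups. The two groups therefore practise identically apart from the card.

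**(a) Split on Q11a only (the strictly circular case).** The other 16 items have probability p in both groups. Users already hold one point and need at least 13 of 16; non-users need at least 14 of 16. At p = 0.90, the probabilities of 13, 14, 15 and 16 are 0.1423, 0.2745, 0.3294 and 0.1853.
- Users: sum of all four = 0.932.
- Non-users: sum of the last three = 0.789.
- The built-in gap in mean score is exactly 1 point.

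**(b) Split on receipt, worst case.** Every non-recipient scores 0 on Q11a-c; recipients give a desirable response to each with probability 0.95 (assumed).
- Non-recipients: p^14 = 0.90^14 = 0.229.
- Recipients: P[Bin(14, 0.90) + Bin(3, 0.95) ≥ 14] = 0.8574 × 0.9559 + 0.1354 × 0.8416 + 0.0071 × 0.5846 + 0.0001 × 0.2288 = 0.938.
- The built-in gap in mean score is 3 × 0.95 = 2.85 points.

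**(c) As (b), but Q11b can be met without a card.** Non-recipients score 0 only on Q11a and Q11c and need at least 14 of 15: 0.3432 + 0.2059 = 0.549.

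**Range over p (pass rates).**

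| p | (a) user vs non-user | (b) recipient vs non-recipient, worst case | (c) non-recipient, Q11b met without a card |
|---|---|---|---|
| 0.85 | 79.0% vs 56.1% | 82.2% vs 10.3% | 31.9% |
| 0.90 | 93.2% vs 78.9% | 93.8% vs 22.9% | 54.9% |
| 0.95 | 99.3% vs 95.7% | 99.1% vs 48.8% | 82.9% |

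**Without the card items.** On the 14 remaining items both groups have the same pass probability at any p, so the built-in gap is zero by construction. With a cut of 12/14 it is 64.8%, 84.2% and 97.0% at p = 0.85, 0.90 and 0.95 in both groups.

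**The case against.** The strongest reply is that the protocol does not fix this analysis. Stratification may be performed and groups can be compared; neither section says that the contrast uses the 14/17 cut, or how several materials combine into received or not received. That stands, and it means no primary estimate is at stake. The protocol does, however, fix the 17-item score, the cut, the double role of Q11a and the contrast itself, and the problem lies in how these combine.

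A reader might infer that the whole received-or-used comparison is circular. The documents do not support that. Receipt is asked separately in Q16.1a, and Q11a is one of five utilisation questions, so strict circularity is confined to a split on Q11a.

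A reader might also take 93.8% versus 22.9% as the expected artefact. It is an upper bound. Groups may be formed on the brochure or checklists; section 6 says the materials are also available online, so reporting no supply does not prove having no card; section 8.9.2 concedes that recall may be wrong; Sometimes counts as desirable; and advice to report symptoms can be given without a card.

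Finally, giving the card and reminding patients to carry it belong to Key Risk Message 9, so part of any gap is real programme behaviour. This is right, and it is why the 17-item score should be kept. It does not justify letting card items drive an inference about the other practices. Section 8.9.1 already calls attribution limited, and section 8.7.4 reports each item separately, but it does not promise that by stratum.

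**Conclusion.** The point holds in a limited form. Applying the protocol's adherence score to strata of receipt or utilisation builds in a difference favouring the programme: strictly circular for card utilisation through Q11a, a structural dependence for receipt. At 90% desirable per item the gap in pass rate is 93.2% − 78.9% = 14.3 percentage points when splitting on Q11a alone. In the worst case for receipt it is 93.8% − 22.9% = 70.9 points, falling to 93.8% − 54.9% = 38.9 points if Q11b needs no card. These figures rest on independent items, equal practice otherwise and, for receipt, 95% desirable card responses among recipients; groups built on other materials would dilute them.

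The comparison is optional and descriptive. The knowledge comparison, the pooled 17-item result, the per-question results and the success criterion are unaffected. The change is worth making because this is the only contrast offered in place of a baseline.

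**What to change.** In sections 8.7.1 and 8.9.1, state that for any comparison by receipt or utilisation:
- adherence is also computed on the 14 card-independent items (Q8a-f, Q9a-g, Q11d), and this version is used for any inference about attribution;
- it is summarised as the mean number or proportion of desirable responses, or against a pre-stated cut. A cut of 12/14 (86%) is one choice, somewhat stricter than 14/17 (82%); 11/14 would be 79%;
- Q11a-c are reported separately among HCPs answering Yes to Q16.1a;
- Q11a is not used as both stratifier and outcome.

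The pooled 17-item result and its success criterion stay unchanged. The cost is a short addition to the text and one derived variable from data already collected, with no change to the questionnaire. The contrast between groups will look less favourable.

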8.9.2. Limitation of Human Recall

The HCPs will be asked if they recall having received the aRMM materials. Because the MAH will have no way to verify true receipt of materials (original or current), it is possible that HCPs who report never receiving the materials will have, in fact, received them and vice versa.

8.9.3. Social Desirability

As in all surveys, this survey may promote a social desirability bias, which refers to the tendency of HCPs to give socially desirable/expected responses instead of choosing those reflecting their current knowledge or behaviour.¹⁷ For example, HCPs can provide information gathered online instead of giving their own opinions, or declare a conforming prescribing practice when, in fact, they are not adherent to the aRMMs. Social desirability can affect the validity of survey research findings, but the use of pre-populated items (i.e., response options) in the survey could/tends to reduce this bias.¹⁸

8.9.4. Mode of Survey

HCPs will be offered the opportunity to complete the survey over the telephone, if preferred. However, the MAH does not expect that HCPs who complete the survey via telephone will have systematically better or worse recollection of the aRMM materials than HCPs who complete the survey online. Further, given the small number of surveys that are expected to be completed over the telephone, the MAH does not expect the impact of this bias to be large.

8.9.5. Generalisability

Generalising the results of a survey to the population of interest assumes that the HCPs who provided data are a representative sample of the population. In an attempt to assess this assumption, the distribution of select HCP characteristics (e.g., country, specialty, and any other available characteristics present in the OneKey database) will be compared between HCPs who responded and HCPs who did not respond to the survey study invitation. If survey non-response (i.e., failure to contact or elicit participation from eligible HCPs) creates non-response bias (because respondents differ from non-respondents), survey estimates of means, proportions, and other population parameters might be biased. Because information on important characteristics of non-respondents will be limited, our ability to assess

generalisability may be limited, especially if the response rate is low. Additionally, for the subgroup analyses, when the total number of HCPs from a particular subgroup (e.g., dermatologists) is less than 30, generalisability of study results to all HCPs of that subgroup in the target population (e.g., dermatologists in Europe) may not be possible.

8.9.6. Reaching the Minimum Target Sample Size

Reaching the minimum target sample size of 300 HCPs (i.e., completed surveys) for each survey (RA/PsA and UC) might not be feasible for a number of reasons. First, while the survey will not begin in each survey country until at least 6 months has passed between Xeljanz reimbursement and the start of data collection, it is possible that market penetrance may still be low at the start of data collection, especially for the survey countries where this interval is shorter (i.e., Romania for the PsA and UC indications). Low market penetrance means fewer HCPs with experience prescribing Xeljanz and thus a smaller base of HCPs eligible to participate in the survey.

Additionally, feasibility work suggests that offering an honorarium to participating HCPs is not feasible in Germany, the Netherlands, Sweden, and the UK. This may result in a lower HCP response rate for those countries. Indeed, a similar aRMM evaluation study conducted by the MAH in 10 European countries (9 of which had no honoraria) experienced a total response rate of only 1.7%.¹²

Finally, an unknown proportion of specialist HCPs are expected to (1) manage patients indicated for Xeljanz treatment on a regular basis and (2) have the necessary certification to prescribe Xeljanz. Because the OneKey database does not contain this information, the exact number of HCPs anticipated and/or certified to prescribe Xeljanz for patients with RA, PsA, and/or UC cannot be determined prior to the start of the study.

Despite these limitations, the MAH will make every effort to reach the minimum target sample size as described in [Section 8.6.5](#) (Approaches for Increasing Response Rates). Regardless of whether the minimum target sample size is reached, all available results will be provided to the PRAC by the timelines proposed (barring administrative delays in protocol approval, local Health Authority and/or Ethics Committee approvals, other competent authorities, Xeljanz reimbursement dates, and/or timely distribution of the current aRMM materials).

